10.6 Pharmacodynamic Analyses

Provided that the data allows, PD and immunogenicity data from all patients may be analyzed using linear and/or nonlinear fixed and mixed effects models as appropriate. Pharmacodynamic and immunogenicity data will be summarized by dose, drug concentrations, and time from dose

for each schedule of administration. Potential PD markers and immunogenicity versus time data will be presented graphically for each patient and summarized by dose and schedule of administration. Absolute and/or percent change from baseline for the PD markers may also be evaluated. Data may be log-transformed prior to summarizing if necessary. The interpatient and inpatient variability of the PD markers and immunogenicity responses may also be assessed where appropriate. Baseline measurements may be evaluated as potential covariates to assess their relationship to relevant PD responses.

10.7. Pharmacokinetic/Pharmacodynamic Analyses

In addition to a standard noncompartmental assessment, and provided that the data allows, the LY3164530 serum concentration-time data may be evaluated by model-based approaches as warranted. Additional analyses, such as exposure-response modeling using the efficacy endpoints, may also be explored.

Additional exploratory analyses may be performed if warranted by the data.

10.10 Interim Analyses

Since this is a dose-escalation study, data will be reviewed on an ongoing basis during the study until the RP2D is determined. The purpose of these ongoing reviews is to evaluate the safety data at each dose level. A review of the data will be completed approximately after ~~5~~ 6 patients have been treated for at least 1 cycle at a dose level without a cohort analysis.

An interim analysis will be triggered when at least 4-15 patients have been dosed at a given dose level for 1 cycle of treatment to evaluate the safety and tolerability of LY3164530. The interim analysis may include, but are not limited to, an assessment of available safety, PK, and PD data.

Enrollment may continue during the interim analysis and the dose escalation rules as outlined in Figure JNBA.1 will continue to be followed.

Additional interim analyses may be triggered and may include, but are not limited to, assessment of available safety, PK, and PD data.

12 References

...

Attachment 1 Protocol JNBA Study Schedule

Baseline Schedule

Study Period	Baseline		
Cycle	BL		
Visit	0		
Duration	Up to 28 days		
Relative Day to C1D1	≤28	≤14	≤7

Procedure Category	Procedure				Comments
Lab/ Diagnostic Tests	Local hematology		X		
	Local chemistry		X		
	Local coagulation		X		
	Local urinalysis		X		
	Local pregnancy test		✗	✕	Must be done ≤147 days prior to the first dose of study drug if patient is a woman of child-bearing potential. May be urine or serum specimen.
	Central ECG		X		Triplicate ECG.
	Biopsy of pretreatment tumor tissue		X		Unless the Sponsor and investigator document that the biopsy may be omitted; sample should be taken only after study eligibility is confirmed
	Archived tumor tissue (only if available)		X		Only for those patients that meet inclusion/exclusion criteria
	Tumor markers		X		Only if appropriate for the tumor type of the patient.
	Exploratory biomarker blood sample for pharmacogenomics		X		If possible, this sample should be collected at the time on the same day as of the biopsy.
	Immunogenicity sample		X		

During Treatment Study Schedule

		Study Period	Study Treatment Period														
		Cycle/Visit	1						2				3-Xa				
		Duration	28 days						28 days				28 days				
		Relative Day within Dosing Cycle	1	2	3	8	15	22	1	8	15	22	1	8	15	22	
Procedure Category	Procedure															Comments	
Physical Examination	Physical exam (including weight and skin inspections)	X						X				X				May be completed up to 7 days prior to the treatment infusion.	
	Vital signs	X			X	X	X	X	X	X	X	X	X*	X	X*	Includes blood pressure, pulse, and temperature. For Cycles 1-2, At a minimum, vital signs should be obtained prior to infusion, during infusion, and at 1 hour EOI (Section 7.2.4.1). In Cycle 3-X, vital signs should be taken predose and when clinically indicated. * Only need to be collected for patients on Schedule 2	
	ECOG performance status	X						X				X				May be completed up to 7 days prior to the treatment infusion	
Lab/Diagnostic Tests	Local hematology	X	X	X	X	X	X	X	X	X	X	X		X		On CID1, both pre-dose and post-dose samples should be drawn. See Attachment 4. In Cycles 3-X, M may be drawn up to 1 day prior to the planned assessment. On CID1, post-dose samples should be drawn. See Attachment 4 Schedule 2: In Cycle 3-X, if clinically significant changes are observed, hematology should be obtained at least weekly until no longer clinically significant.	
	Local chemistry	X	X	X	X	X	X	X	X	X	X	X		X		On CID1, both pre-dose and post-dose samples should be drawn. See Attachment 4. Beginning with Cycles 3-X, lab m May be drawn up to 1 day prior to the planned assessment. On CID1, post-dose samples should be drawn. See Attachment 4 Schedule 2: In Cycle 3-X, if clinically significant changes are observed, chemistry should be obtained at least weekly until no longer clinically significant.	
	Local Urinalysis	X						X				X				May be assessed up to 3 days prior to the planned assessment.	
	PK sampling				X					X				X		See Attachment 3.	
	Immunogenicity Sample	X						X				X				In addition to the scheduled samples, if a patient should have an infusion-related reaction to LY3164530, all attempts should be made to obtain	

																	immunogenicity sample as close to the onset of the event as possible, at the resolution of the event and 28 days following the event. A portion of the sample taken for immunogenicity testing may be used for PK analysis.
	MET and EGFR ECD pharmacodynamic samples	X	X			X		X		X		X					See Attachment 3 .
	MET and EGFR ligands pharmacodynamic samples,	X	X			X		X		X		X					See Attachment 3 .

During Treatment Study Schedule

		Study Period	Study Treatment Period														
		Cycle/Visit	1						2				3-X				
		Duration	28 days						28 days				28 days				
		Relative Day within Dosing Cycle	1	2	3	8	15	22	1	8	15	22	1	8	15	22	
Procedure Category	Procedure															Comments	
Lab/ Diagnostic Tests (cnt'd)	Proteomic blood sample	X	X			X		X		X		X				See Attachment 3 . Sample is only collected through Cycle 6.	
	Stored sample for pharmacogenomics	X														Collect once. Sample can be collected at any time if not collected on C1D1.	
	Exploratory biomarker blood sample for pharmacogenomics	X										X				Sample to be collected C7D1.	
	Central ECG	X	X	X	X	X	X	X	X	X	X	X	X*	X	X*	In Cycle 1, triplicate ECGs collected predose, at EOI, 2 hours EOI, and 6 hours EOI on the day of dosing . If possible, obtain prior to any associated blood draws. In Cycles 2-X, single ECGs should be obtained predose on the day of dosing. On non-dosing days,the ECG may be obtained anytime, but if possible they should be obtained near to the same time of day as the C1D1 ECG. See Attachment 4 . *Schedule 2 only.	
	Tumor markers							X				X				If applicable to tumor type of the patient; may be drawn up to 3 days prior to the planned assessment.	
	Optional tumor biopsy										X						
Tumor Assessment	Tumor measurement (palpable or visible)										X			X		Perform at least every 8 weeks at the end of every even cycle .	
	Radiologic imaging according to RECIST										X			X	X	The same method of imaging used at baseline should be used for each subsequent assessment. Perform at least every 8 weeks other cycle (approximately every 8 weeks) between D22-28 . May be omitted if patient has clear signs of progressive disease.	
Adverse Events Collection/CTCAE Grading				X						X				X			
Concomitant Medication Notation				X						X				X			
	LY3164530 – Schedule 1	X				X		X		X		X		X			

	LY3164530 – Schedule 2	X			X										
--	-------------------------------	----------	--	--	----------	----------	----------	----------	----------	----------	----------	----------	----------	----------	--

^a Following discussion and agreement from the Sponsor, the frequency of some assessments may be reduced for patients that have been on treatment for more than 1 year and are continuing to derive benefit from treatment. This decision will be documented in writing.

Post-Treatment Discontinuation Schedule

Procedure Category	Procedure	Post-discontinuation Follow-Up	Comments
	Study Period		
	Visit 801		Post-treatment discontinuation follow-up should begin after the last dose of study therapy or, if study therapy has been omitted for an extended period, the date it is decided that the patient will not restart study therapy.
	Duration	28 ±5 days	
	Relative Day	28	
Physical Examination	Weight	X	
	Vital signs	X	Includes blood pressure, pulse, and temperature.
	ECOG performance status	X	
Tumor Assessment	Tumor measurement (palpable or visible)	X	Performed if lesion is assessed as target or non-target. Not required if progressive disease is documented while on treatment.
	Radiologic imaging according to RECIST	X	The same method of imaging used at baseline should be used for each subsequent assessment. Not required if progressive disease is documented while on treatment or if there are clear signs of clinical progression.
Adverse Events Collection/CTCAE Grading		X	After Visit 801, only study protocol- or drug-related events are reported. If a patient has an ongoing AE or SAE possibly related to LY3164530 (eg, abnormal electrolytes), the patient should be followed until the event is resolved, the event is no longer considered to be drug-related, the event becomes stable or returns to baseline, a new treatment is initiated for the patient, or the patient dies or is lost to follow-up. Any subsequent follow-up(s) for AEs will be no more than 28 days ±5 days in duration.
Concomitant Medication Notation		X	
	Local hematology	X	
	Local chemistry	X	Particular focus should be placed on patients that have abnormal electrolytes, as electrolyte depletion is known to occur for >6 weeks after EGFR monoclonal antibody therapy.
	Central ECG	X	Single ECG.
	Tumor markers	X	If applicable to tumor type of the patient.
	Optional tumor biopsy	X	From patients willing to consent.

Lab/ Diagnostic Tests	Exploratory biomarker blood sample	X	
	PK sample	X	
	Immunogenicity sample	X	In addition to the scheduled sample, if a patient should have an infusion reaction to LY3164530, all attempts should be made to obtain immunogenicity sample as close to the onset of the event as possible, at the resolution of the event, and 30 days following the event. If a patient requires subsequent follow-ups (eg, for an ongoing AE), an immunogenicity sample should be obtained, if possible. A portion of the sample taken for immunogenicity testing may be used for PK analysis.
	MET and EGFR ECD pharmacodynamic samples	X	
	MET and EGFR ligand pharmacodynamic samples	X	
	Proteomic blood sample	X	Only if patient discontinues prior to Cycle 6.

Abbreviations: AE = adverse event; BL = baseline; C = cycle; CT = computed tomography; CTCAE = Common Terminology Criteria for Adverse Events; D = day; ECD = extracellular domain; ECG = electrocardiogram; ECOG = Eastern Cooperative Oncology Group; eCRF = electronic case report form; EGFR = epidermal growth factor receptor; EOI = end of infusion; HPV = human papillomavirus; MET = mesenchymal-epithelial transition factor; MRI = magnetic resonance imaging; PK = pharmacokinetic; RECIST = Response Evaluation Criteria in Solid Tumors; SAE = serious adverse event.

Attachment 3 Protocol JNBA Pharmacokinetic and Pharmacodynamic Sampling Schedule

Pharmacokinetic and Pharmacodynamic Sampling for Schedule 1

Cycle	Day	Collection Time	PK Sampling Time	MET ECD and EGFR ECD ^a	MET and EGFR Ligands ^a	Proteomic Blood Sample ^a
1 and 2	1	Predose	X	X	X	X
	1	Mid-infusion	X			
	1	End of infusion	X	X	X	X
	1	2 hours post end of infusion	X			
	1	4 hours post end of infusion	X			
	1	6 hours post end of infusion (Cycle 1 only)	X			
	2	24 ±4 hours post-end of infusion (Cycle 1 only)	X	X	X	X
	3	Anytime during day (Cycle 1 only)	X			
	8±1	Anytime during day	X			
	15	Predose	X	X	X	X
	15	End of infusion	X	X	X	X
	15	2 hours post end of infusion (Cycle 1 only)	X			
	15	4 hours post end of infusion (Cycle 1 only)	X			
	15	6 hours post end of infusion (Cycle 1 only)	X			
	22±2	Anytime during day (Cycle 1 only)	X			
3-6	1	Predose	X	X	X	X
	1	End of infusion	X			
Follow-ups		Occurs on the day the follow-ups occur.	X	X	X	

Abbreviations: ECD = extracellular domain; EGFR = epidermal growth factor receptor; MET = mesenchymal-epithelial transition factor; PK = pharmacokinetic; V = volume of distribution.

- a Samples are requested to be taken immediately before the dose and immediately after the end of the LY3164530 infusion. Aberrations to specified sampling times will not be considered protocol deviations as long as the samples are taken and the actual sampling time is recorded. It is essential that the actual times of LY3164530 dose and samples are recorded accurately on the appropriate forms.

Pharmacokinetic and Pharmacodynamic Sampling for Schedule 2

Cycle	Day	Collection Time	PK Sampling Time	MET ECD and EGFR ECD^a	MET and EGFR Ligands^a	Proteomic Blood Sample^a
1 and 2	1	Predose	X	X	X	X
	1	Mid-infusion	X			
	1	End of infusion	X	X	X	X
	1	2 hours post end of infusion	X			
	1	4 hours post end of infusion	X			
	1	6 hours post end of infusion	X			
	2	24 ±4 hours post-end of infusion	X	X	X	X
	3	Anytime during day	X			
	8	Predose	X			X
	8	End of infusion (Cycle 1 only)	X			X
	15	Predose (Cycle 1 only)	X	X		X
	15	End of infusion (Cycle 1 only)	X			X
	22	Predose(Cycle 1 only)	X	X	X	X
	22	End of infusion (Cycle 1 only)	X	X	X	X
	22	2 hours post end of infusion (Cycle 1 only)	X			
	22	4 hours post end of infusion (Cycle 1 only)	X			
	22	6 hours post end of infusion (Cycle 1 only)	X			
	23	24 ±4 hours post-end of infusion (Cycle 1 only)	X			
	24	Anytime during day (Cycle 1 only)	X			
3-6	1	Predose	X	X	X	X
	1	End of infusion	X			
Follow-ups		Occurs on the day the follow-ups occur.	X	X	X	

Abbreviations: ECD = extracellular domain; EGFR = epidermal growth factor receptor; MET = mesenchymal-epithelial transition factor; PK = pharmacokinetic; V = volume of distribution.

^a Samples are requested to be taken immediately before the dose and immediately after the end of the LY3164530 infusion. Aberrations to specified sampling times will not be considered protocol deviations as long as the samples are taken and the actual sampling time is recorded. It is essential that the actual times of LY3164530 dose and samples are recorded accurately on the appropriate forms.

Attachment 4 Protocol JNBA ECG, Chemistry, and Hematology Collection Schedule

Schedule 1

Cycle	Day	Collection Time	Central TriPLICATE ECG	Central Single ECG	Local Hematology	Local Chemistry	
Screening			X		X	X	
1	1	Predose	X		X	X	
	1	EOI (+ 10 min)	X		X ^a	X ^a	
	1	2 ±0.25 hours EOI	X				
	1	6 ±0.25 hours EOI	X				
	2	24 ±4 hours EOI	X		X ^a	X ^a	
	3	48 ±4 hours EOI	X		X ^a	X ^a	
	8		X		X	X	
	15	Predose	X		X	X	
	15	EOI (+ 10 min)	X				
	15	2 ±0.25 hours EOI	X				
	15	6 ±0.25 hours EOI	X				
	22		X		X	X	
	2	1	Predose		X	X	X
		8			X	X	X
		15	Predose		X	X	X
22				X	X	X	
3-X	1	Predose		X	X	X	
	15	Predose		X	X	X	
Follow up	28			X	X	X	

Abbreviations: ECG = electrocardiogram; EOI = end of infusion; min = minute.

^a If an abnormality in hematology or chemistry is consistently observed in the 48 hours following the end of the first infusion, additional post-infusion laboratory samples (EOI, and 24 hours and 48 hours after EOI) must be repeated for subsequent infusions until they are normal or return to baseline levels.

Schedule 2

Cycle	Day	Collection Time	Central TriPLICATE ECG	Central Single ECG	Local Hematology	Local Chemistry
Screening			X		X	X
1	1	Predose	X		X	X
	1	EOI (+ 10 min)	X		X^a	X^a
	1	2 ±0.25 hours EOI	X			
	1	6 ±0.25 hours EOI	X			
	2	24 ±4 hours EOI	X		X^a	X^a
	3	48 ±4 hours EOI	X		X^a	X^a
	8	Predose	X		X	X
	8	EOI (+ 10 min)	X			
	8	2 ±0.25 hours EOI	X			
	8	6 ±0.25 hours EOI	X			
	15	Predose		X	X	X
	22	Predose		X	X	X
2-X	1	Predose		X	X	X
	8	Predose		X	X^b	X^b
	15	Predose		X	X	X
	22	Predose		X	X^b	X^b
Follow up	28			X	X	X

Abbreviations: ECG = electrocardiogram; EOI = end of infusion; min = minute.

4.1. Primary Objective

The primary objective of this study is to determine a recommended phase 2 dose (RP2D) of LY3164530 that may be safely administered to patients with advanced or metastatic cancer.

4.2. Secondary Objectives

The secondary objectives of this study are:

- to characterize the safety and toxicity profile of LY3164530
- to estimate the pharmacokinetic (PK) parameters of LY3164530
- to document any antitumor activity observed with LY3164530.

4.3. Exploratory Objectives

The exploratory objectives of this study are:

- to explore the effect of LY3164530 on pharmacodynamic (PD) markers
- to identify exploratory biomarkers associated with tumor response and/or safety.

5. Study Design

5.1. Summary of Study Design

Study I7H-MC-JNBA (JNBA) is a multicenter, nonrandomized, open label, dose escalation Phase 1 study of IV LY3164530 in patients with advanced and/or metastatic cancer. Eligible patients will receive LY3164530 as an infusion on Days 1 and 15 of each cycle. A cycle will consist of 28 days.

The planned duration of treatment is 2 cycles. Patients who are receiving benefit from study drug may continue to be treated with LY3164530 until 1 or more of the criteria for discontinuation have been fulfilled (Protocol Section 6.3.1).

5.2. Determination of Sample Size

To determine an RP2D of LY3164530 that may be safely administered to patients with advanced or metastatic cancer, an adequate patient sample size is required. A sufficient sample size will allow for an accurate evaluation of the relationship between exposure and toxicity, as well as an evaluation of the relationship between exposure and pharmacological effects using descriptive statistics and appropriate modeling techniques, if data warrant.

Dose escalation will be driven by a modified toxicity probability interval (mTPI) method. The RP2D will be determined once at least 10 patients, but no more than 20, are treated at a dose level that is at or below the maximum tolerated dose (MTD). The actual sample size for Study JNBA depends on the incidence of dose-limiting toxicities (DLTs) and is anticipated to be approximately 50 patients.

5.3. Method of Assignment to Treatment

Patients who meet all criteria for enrollment will be assigned to receive LY3164530 in this study. Before each patient's enrollment into the study, an eligibility check must be conducted between the investigational site and Eli Lilly and Company (Lilly) clinical research personnel to confirm that each patient meets all enrollment criteria. Upon confirmation of eligibility, the Sponsor will confirm the dose, infusion duration, and identification number assignment for each patient.

6. A Priori Statistical Methods

6.1. General Considerations

The analyses for this study will be descriptive, except for possible exploratory analyses as deemed appropriate. Data analyses will be provided by dose levels and for all patients combined wherever appropriate. For continuous variables, summary statistics will include number of patients (N), mean, median, standard deviation (SD), standard error (SE), minimum, and maximum. Categorical endpoints will be summarized using N, frequency, percentages, and associated SE.

Exploratory analyses of the data that are not described in the protocol will be conducted as deemed appropriate.

Any change to the data analysis methods described in the protocol will require an amendment ONLY if it changes a principal feature of the protocol. Any other change to the data analysis methods described in the protocol and the justification for making the change will be described in the clinical study report (CSR).

The interpretation of the study results will be the responsibility of the investigator with the Lilly CRP and/or CRS, pharmacokineticist, and statistician. The CRP and/or CRS and statistician will also be responsible for the appropriate conduct of an internal review for both the final study report and any study-related material to be authorized by Lilly for publication.

The following data handling conventions will be used in the analysis:

Table JNBA.6.1. Data Handling Conventions and Rules

Term	Definition or Rule
Study Day	If assessment is on or after date of first dose then (date of assessment) – (date of first study drug dose) +1
	If assessment precedes first dose of drug then (date of assessment) – (date of first study drug dose)
	There is no study day 0. Study day 1 is the date of first dose and study day -1 is the day before the first dose.
Cycle Day	If assessment is on or after date of first dose in the cycle then (date of assessment) – (date of first study drug dose in cycle) +1
	If assessment precedes first dose of drug in a cycle then (date of assessment) – (date of first study drug dose in cycle)
	There is no cycle day 0. Cycle day 1 is the date of first dose in the cycle and cycle day -1 is the day before the first dose.
Baseline	For change from baseline analyses, baseline value is defined as the last reported measure on or before the first dose (prior to the dose administration). For change from baseline within a cycle, the measure prior to the first dose of that cycle is baseline. If more than one pre-dose measure is available, they may be averaged if appropriate.
Entered	Patients who sign the informed consent document (ICD).
Enrolled	Patients who have been assigned to a treatment (assigned means they received ≥ 1 dose for this study).

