7.6.1. Evaluable Patients

Patients who withdraw from the study before receiving study drug will be replaced and will not be included in the safety or efficacy assessments. Safety analyses will be conducted on all patients who have been exposed to study drug, regardless of whether they are deemed evaluable for the assessment of a dose level.

Any patient who is discontinued from the study before completing 1 cycle of LY3164530 treatment will be deemed non-evaluable for assessment of a dose level, unless they experience a DLT prior to withdrawal. However, patients who receive all doses of LY3164530, but discontinue from study drug before the end of Cycle 1, will be considered evaluable for the assessment of a dose level, provided it can be documented whether the patient experienced a DLT during Cycle 1.

If the patient is noncompliant during Cycle 1 due to reasons other than drug-related toxicity, he or she will be considered non-evaluable and may be replaced.

Patients that require a dose reduction or omission during Cycle 1 or have a dosing delay of more than 3 days for reasons other than a study drug-related AE may be deemed non-evaluable for DLT assessment.

Nonevaluable patients may be replaced to ensure that enough patients complete 1 cycle of therapy at each dose level, unless accrual to that cohort has stopped due to a DLT.

Patients who are not evaluable for PK, but who complete 1 cycle of therapy, may be replaced upon consultation with the investigator(s) and the Lilly CRP or CRS to ensure adequate PK data, unless accrual to that cohort has stopped due to a DLT.

8. Safety, Pharmacokinetic, Pharmacodynamic, and Efficacy Data Collection

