10.4. Safety Analyses

All patients who have been exposed to LY3164530 will be evaluated for safety and toxicity. Adverse event terms and severity grades will be assigned by the investigator using CTCAE v 4.03.

Safety analyses will include summaries of the following:

- AEs, including severity and possible relationship to study drug
- dose adjustments (reductions, omissions, and delays)
- laboratory values
- vital signs
- DLTs at each dose level
- ECGs
- Extent of concomitant medications.

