6.3. Handling of Dropouts or Missing Data

Missing data will not be imputed.

Patients who withdraw from the study before receiving study drug will be replaced.

In the following situation, patients will be considered non-evaluable and may be replaced to ensure that enough patients complete 1 cycle of therapy at each dose level, unless accrual to that cohort has stopped due to a DLT:

1. Any patient who is discontinued from the study before completing 1 cycle of LY3164530 treatment unless they experience a DLT prior to withdrawal
2. Patients who are not evaluable for PK

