6.6. Population for Analysis

Safety analyses will be conducted on all patients who have received at least one dose of LY3164530.

Pharmacokinetic analyses will be conducted on patients who have received at least one dose of LY3164530 and have sufficient samples collected to allow the estimation of LY3164530 PK parameters.

Pharmacodynamic analyses will be conducted on patients who have received at least one dose of LY3164530 and have sufficient samples collected to allow the assessment of pharmacodynamics.

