6.13. Safety Analyses

All patients who receive at least 1 dose of LY3164530 will be evaluated for safety and toxicity. Adverse event (AE) terms and severity grades will be assigned by the investigator using National Cancer Institute Common Terminology Criteria for Adverse Events (NCI CTCAE) Version 4.03.

Safety analyses will include summaries of the following:

- Adverse events, including severity and possible relationship to study drugs
- Dose delays and dose adjustments
- Laboratory values
- Vital signs
- Dose-limiting toxicities at each dose level
- Electrocardiogram readings
- Deaths on treatment and within 28 +/- 5 days of treatment discontinuation

Hospitalizations and transfusions during the study treatment period or during the 28 +/- 5 days - day postdiscontinuation follow-up period will be summarized.

Dose Limiting Toxicity

Dose-limiting toxicity is defined as an AE during Cycle 1 that is considered by the investigator to be at least possibly related to LY3164530 and fulfills any one of the following criterion using the NCI CTCAE Version 4.03:

- \geq Grade 3 non-hematological toxicity. Exceptions will be made for:

- nausea, vomiting, diarrhea, and constipation that can be controlled with treatment. Grade 3 and Grade 4 nausea, vomiting, or diarrhea should be considered DLTs if persisting more than 48 hours despite supportive intervention.
 - Grade 3 rash that resolves with treatment to \leq Grade 2 within 8 days
 - Grade 3 or 4 asymptomatic electrolyte abnormalities that respond to standard treatment
 - Grade 3 elevations of ALT and/or AST lasting fewer than 8 days, without evidence of other hepatic injury, in the setting of preexisting hepatic metastasis. Baseline elevation of these values may not be considered a DLT if agreed by the study investigator and Lilly CRP/CRS.
- Grade 4 neutropenia or leukopenia, of >7 days duration.
 - Grade 4 thrombocytopenia of any duration.
 - Grade 3 thrombocytopenia with bleeding.
 - Any febrile neutropenia.
 - Any other significant toxicity deemed by the primary investigator and Lilly clinical research personnel to be dose limiting (eg, any toxicity that is possibly related to the study drug that requires the withdrawal of the patient from the study during Cycle 1).

DLT-Equivalent Toxicities

A DLT-equivalent toxicity is defined as an AE occurring in Cycle 2 and beyond that would have met the criteria for a DLT if it had occurred during Cycle 1.

Dose Escalation Method

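### The only planned precision figure for the DLT rate is an SE that is 0 when no DLT is seen, and its default denominator includes patients the protocol calls non-evaluable

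*SAP*

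**What the plan says.** **Statistic.** The general sections of both documents (SAP 6.1, Protocol 10.1) contain the same sentence: "Categorical endpoints will be summarized using N, frequency, percentages, and associated SE". DLTs appear as one item in each list of safety summaries: "Dose-limiting toxicities at each dose level" in SAP 6.13 and "DLTs at each dose level" in Protocol 10.4. Neither list attaches a statistic. The only confidence intervals planned anywhere are 90% intervals for PK geometric mean ratios (SAP 6.12.1, Protocol 10.5).

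**Population.** SAP 6.6 states: "Safety analyses will be conducted on all patients who have received at least one dose of LY3164530". Protocol 7.6.1 agrees, and says that this holds "regardless of whether they are deemed evaluable for the assessment of a dose level". The same protocol section then removes some dosed patients from dose-level assessment:
- those who leave before completing Cycle 1 without a DLT, with an exception for patients who had all their doses and whose DLT status is documented;
- those noncompliant in Cycle 1 for reasons other than drug-related toxicity;
- those with a Cycle 1 dose reduction, omission or delay of more than 3 days not due to a drug-related AE, who "may be deemed non-evaluable for DLT assessment".

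SAP 6.6 defines safety, PK and PD populations but no DLT-evaluable set. SAP 6.3 has its own two-item list of non-evaluable patients: early discontinuation without a DLT, and "Patients who are not evaluable for PK".

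**The concern.** The primary objective is a recommended Phase 2 dose (RP2D), and the design targets a 30% DLT rate. The observed DLT rate by dose is therefore central evidence in the study report. Two things weaken how it will be shown.

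First, the binomial SE breaks down at the edge of the scale. A dose with 0 DLTs in 3 patients and one with 0 in 20 would both be reported as 0% with SE 0. Taken literally, that claims complete certainty in both cases.

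Second, the rate would by default be computed in every dosed patient. Under Protocol 7.6.1 a patient who leaves early without a DLT is not informative about the dose. Counting such patients as DLT-free lowers the reported rate. Because SAP 6.3 and Protocol 7.6.1 also list different non-evaluable patients, two programmers could derive different evaluable counts from the same data.

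**Working it through.** **Inputs**
- Summary rule: N, frequency, percentage and SE (SAP 6.1, Protocol 10.1).
- Patients per dose: a minimum of 3 (Protocol 7.2.2.3, SAP 6.13); between 10 and 20 at the RP2D (Protocol 7.2.3, SAP 6.13.1).
- Target DLT rate: 30% (Protocol 7.2.2.3, SAP 6.13).
- Assumed: the usual binomial SE, since neither document gives a formula; a two-sided 95% level for the exact interval; a true rate of 10% to represent a low-toxicity dose.

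The plan states no precision figure for the DLT rate, so there is none to reproduce.

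**Step 1: SE and exact limit when no DLT is seen.** SE = √(p(1−p)/n), where p is the observed rate. With p = 0, SE = 0 at every n. The Clopper-Pearson upper limit at 0/n is 1 − 0.025^(1/n). For n = 3 this is 1 − 0.292 = 0.708.

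**Step 2: how often this happens.** The chance of zero DLTs at true rate π is (1−π)^n. For n = 6 it is 0.9^6 = 0.531 at 10% and 0.7^6 = 0.118 at 30%.

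| n | SE at 0/n | Exact 95% upper limit | P(0 DLTs), true 10% | P(0 DLTs), true 30% |
|---|---|---|---|---|
| 3 | 0 | 70.8% | 72.9% | 34.3% |
| 6 | 0 | 45.9% | 53.1% | 11.8% |
| 10 | 0 | 30.8% | 34.9% | 2.8% |
| 15 | 0 | 21.8% | 20.6% | 0.5% |
| 20 | 0 | 16.8% | 12.2% | 0.1% |

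At n = 3, 6 and 10 the exact limit is still above the 30% target while the SE is 0. At the target rate and RP2D sample sizes, zero DLTs is rare.

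**Step 3: denominator.** The documents give no count of non-evaluable patients, so the counts below are assumed.
- Two non-evaluable patients replaced, giving 12 treated, 10 evaluable and 3 DLTs: 3/12 = 25.0% (exact 5.5–57.2%) against 3/10 = 30.0% (6.7–65.2%).
- No replacement, 10 treated and 3 DLTs: 30.0% in all treated. With 1, 2 or 3 of the 10 non-evaluable it is 3/9 = 33.3% (7.5–70.1%), 3/8 = 37.5% (8.5–75.5%) or 3/7 = 42.9% (9.9–81.6%).

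**Step 4: the two evaluability lists**

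| Case | Protocol 7.6.1 | SAP 6.3 |
|---|---|---|
| Early discontinuation, no DLT | Non-evaluable (one exception) | Non-evaluable |
| Noncompliance in Cycle 1, not drug toxicity | Non-evaluable | Not listed |
| Cycle 1 reduction, omission or delay over 3 days, not a drug-related AE | May be non-evaluable | Not listed |
| Not evaluable for PK | Replacement allowed after 1 cycle; not called non-evaluable for DLT | Under the same non-evaluable heading |

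**The case against.** The strongest case against is that little depends on this SE. The analyses are declared descriptive. N and frequency are printed, so 0/3 and 0/20 can be told apart and any reader can compute an exact interval. SAP 6.1 also allows added exploratory analyses. Dose decisions come from the mTPI grid, which already depends on n, and every zero-DLT cell there says escalate, so a zero SE mostly falls at doses the trial moves past. All of this stands and limits the weight of the point. It does not remove it: a reader can rebuild the interval only if the denominator is the right one, and an RP2D may be set below the toxicity limit on PK/PD grounds, where few or no DLTs are plausible.

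A reader might infer four stronger things, none of which the documents support:
- *That escalation or RP2D selection is affected.* Neither uses the SE.
- *That the denominator is unnamed.* It is named in effect. DLTs are listed under safety summaries, and those use all dosed patients. The fault is the conflict with the evaluability rule in Protocol 7.6.1.
- *That the SAP adds PK evaluability where the protocol has none.* Protocol 7.6.1 also lets patients not evaluable for PK be replaced. The SAP differs in giving them the non-evaluable label and in leaving out the noncompliance and dose-modification cases.
- *That the plan will publish poorly covering intervals.* An interval of estimate ± 1.96 SE would cover badly at small n, but nobody planned one, so its coverage is not evidence here.

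**Conclusion.** The point holds as a reporting defect of modest weight. By the general rule, the SE is the only precision figure planned for the DLT rate, and it is 0 at 0/3, 0/6 and 0/10, where the exact 95% upper limits are 71%, 46% and 31%. The problem belongs mainly to low-toxicity doses. Separately, the default all-dosed denominator conflicts with Protocol 7.6.1 and can only lower the rate when non-evaluable patients without a DLT are counted. In the assumed examples the gap is 3 to 13 percentage points, and the upper end requires three of ten patients to be non-evaluable and not replaced.

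This rests on the inference that the general rule governs DLTs, on the usual binomial SE, and on assumed non-evaluable counts.

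**What to change.** - **SAP 6.13:** report the DLT rate by dose and schedule with an exact (Clopper-Pearson) two-sided 95% CI, in place of or beside the SE.
- **SAP 6.6:** define a DLT-evaluable set from Protocol 7.6.1, without using PK evaluability, and make it the denominator. List each dosed patient left out, with the reason. The listing matters because part of the protocol rule is discretionary.
- **SAP 6.3:** bring the non-evaluable list into line with Protocol 7.6.1, keeping replacement for PK separate from evaluability for DLT.

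Protocol 10.1 need not be amended. Under SAP 6.1 a change to the analysis methods "will require an amendment ONLY if it changes a principal feature of the protocol", and adding an interval to a descriptive summary is not such a change. The change and its justification then go in the clinical study report.

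The cost is a few sentences, one population definition and a few lines of code. The downside is wider, somewhat conservative intervals. No escalation rule, RP2D criterion or sample size changes.
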